4.2 JUSTIFICATION FOR DOSE

Each drug will be administered according to the FDA-approved dosing regimen listed in the approved product labeling or provided Investigator's Brochure (IB).

4.3 END OF STUDY DEFINITION

A participant is considered to have completed the study if they were treated for any duration of time, and were followed for survival for 3 years from the date of consent or until death.

5 STUDY ENROLLMENT AND WITHDRAWAL

5.1 INCLUSION CRITERIA

To be eligible to participate in this study, an individual must meet each of the criterion below and the criteria indicated in the selected biomarker/drug cohort appendix:

1. Male or female \geq 18 years of age.

The information contained in this protocol and all other information relevant to this study are confidential and proprietary information of Strata Oncology Inc., except as may be required by federal, state or local laws or regulation, and may not be disclosed to others without prior written permission of Strata.

Page 24 of 56

2. Pathologically confirmed solid tumor.
3. Participants must be able to follow study visit schedule and be willing to provide peripheral blood samples at the indicated time points.
4. CGP results need to be from a test conducted in a CLIA approved laboratory and archival formalin-fixed, paraffin-embedded (FFPE) tumor tissue is required for confirmatory testing of non-Strata test results unless otherwise indicated within the cohort-specific protocol criteria.
5. Biomarker positive for the defined cohort.
6. For individuals with non-primary, treated or stable brain metastases: No evidence of progression (defined as no radiographic evidence of progression) for at least 4 weeks prior to consent.
7. Adequate bone marrow, organ function & laboratory parameters as determined by the treating physician unless otherwise indicated within the cohort-specific protocol criteria.
8. Adequate cardiac function:
 - 8.1. Left ventricular ejection fraction (LVEF) $\geq 50\%$
 - 8.2. QTc interval ≤ 470 ms (females) or ≤ 450 ms (males) average preferred.

5.2 EXCLUSION CRITERIA

An individual who meets any of the following criteria will be excluded from participation in this study:

1. Receiving another anticancer therapy.
2. Major surgery within 4 weeks prior to study entry.
3. Has received a systemic anticancer therapy within 3 weeks of first study dose.
4. Individuals with a history of a second malignancy are ineligible except for the following circumstances. Individuals with a history of other malignancies are eligible if they have been disease-free for at least 3 years or are deemed by the investigator to be at low risk for recurrence of that malignancy. Individuals with the following cancers that have been diagnosed and treated within the past 3 years are eligible: cervical/prostate carcinoma in situ, superficial bladder cancer, non-melanoma cancer of the skin. Patients with other cancers diagnosed within the past 3 years and felt to be at low risk of recurrence should be discussed with the study principal investigator to determine eligibility.
5. Participant has primary central nervous system tumor.
6. A woman of childbearing potential who has a positive urine pregnancy test (within 72 hours) prior to treatment. If the urine test is positive or cannot be confirmed as negative, a serum pregnancy test will be required.
7. Females who are pregnant or nursing or plan to become pregnant or anyone unwilling to use contraception for the duration of treatment.
8. Ongoing toxicity of CTCAE grade ≥ 2 , other than peripheral neuropathy, related to anticancer therapy that was completed within 4 weeks of consent.
9. Ongoing peripheral neuropathy of CTCAE grade ≥ 3 .

The information contained in this protocol and all other information relevant to this study are confidential and proprietary information of Strata Oncology Inc., except as may be required by federal, state or local laws or regulation, and may not be disclosed to others without prior written permission of Strata.

Page 25 of 56

10. History of stroke including transient ischemic attack (TIA) or acute myocardial infarction within 6 months of consent.
11. Participant has a known history of human immunodeficiency virus (HIV), Hepatitis B or known active Hepatitis C virus infection.
12. Medical condition that would place the patient at risk as a result of blood donation, such as bleeding disorder.
13. Any other clinically significant medical condition that, in the opinion of the treating physician, makes participation undesirable, including but not limited to ongoing or active infection, significant uncontrolled hypertension, or severe psychiatric illness.

5.3 CONTRACEPTION

Study medication may have adverse effects on a fetus in utero. Furthermore, it is not known if study medication has transient adverse effects on the composition of sperm.

Participants should be informed that taking the study medication may involve unknown risks to the fetus (unborn baby) if pregnancy were to occur during the study. In order to participate in the study, participants of childbearing potential must adhere to the contraception requirement from the day of study medication initiation (or 14 days prior to the initiation of study medication for oral contraception) throughout the study period up to 210 days after the last dose of study medication. Please refer to the cohort specific package insert for information on contraception requirements. If there is any question that a participant of childbearing potential will not reliably comply with the requirements for contraception, that participant should not be entered into the study.

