4 STUDY DESIGN

4.1 OVERALL DESIGN

Participants who are 18 years of age or older, have been diagnosed with histologically documented solid tumors, have an eligible biomarker profile, and are planned for treatment may be eligible for this study according to the criteria in **Sections 5.1-5.2** and the supplemental criteria in the specific biomarker/drug cohort appendix.

Each biomarker/drug cohort will be described in an appendix to this study protocol. Appendix information includes investigational product overview, rationale for biomarker/drug combination, additional cohort-specific eligibility criteria, study treatment including dosing and administration guidelines, along with known adverse reactions.

After obtaining informed consent, study staff shall assess individual participant eligibility using the criteria in **Sections 5.1-5.2** and the supplemental criteria in the specific appendix they are targeting for enrollment. The designated study staff will enter the participant's details into the electronic data capture (EDC) to support a sponsor-required confirmation of biomarker eligibility. Upon confirmation of eligibility and informed consent procedures, the participant will be formally enrolled into the study. Participants will be treated with the applicable cohort's study drug according to dosing instructions in the approved product labeling or provided Investigator's Brochure (IB).

For participants who exhibit more than 1 eligible biomarker result, the treating physician should determine the most appropriate cohort assignment. Factors for consideration include the drug's dosing and administration guidelines, as well as the commercially available product prescribing instructions or provided IB.

A leftover tumor specimen (if historical comprehensive genomic profiling (CGP) and/or ribonucleic acid (RNA) profiling results are not available for submission) and blood sample for ctDNA analysis will be collected at study entry (prior to therapy start). Blood samples will be

The information contained in this protocol and all other information relevant to this study are confidential and proprietary information of Strata Oncology Inc., except as may be required by federal, state or local laws or regulation, and may not be disclosed to others without prior written permission of Strata.

Page 23 of 56

collected and CT/MRI scans will be performed until treatment discontinuation as outlined in the Study Schedule of Activities (SOA) (**Section 7.2**).

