7.2.2.4 POST-TREATMENT

Study drug will be discontinued upon disease progression or based on physician's discretion as described in **Section 5.5**. Site staff should collect unused study drug and any empty packaging and perform drug accountability upon study drug discontinuation. Participants that discontinue drug will remain on study for 3 years from the date of informed consent for follow-up data entry purposes only. No additional study specific procedures will occur following discontinuation. Participants will continue to see their physician for SOC clinic visits. Site staff will be responsible for collecting and entering the information below in EDC from the participants SOC clinic visits every 3 months.

- Medical history (specifically, disease recurrence and/or survival status)
- Concomitant medications (specifically, anticancer therapies)
- Standard of care procedures, including ECOG status

7.2.3 μMETA COHORTS

Note that μMeta cohorts will not have CT/MRI scans or RECIST 1.1 (or iRECIST) assessments performed.

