8.2.9 REPORTING OF PREGNANCY

The information contained in this protocol and all other information relevant to this study are confidential and proprietary information of Strata Oncology Inc., except as may be required by federal, state or local laws or regulation, and may not be disclosed to others without prior written permission of Strata.

Page 43 of 56

Female participants with the ability to get pregnant will be required to be on a double barrier birth control method for the duration of the trial in all cohorts. Male participants with female partners of child-bearing potential should be advised on birth control approach based on the study drug cohort.

Participants who become pregnant during the study period should not receive any additional doses but will not be discontinued from the study to allow for tracking of event outcome.

Participants will be asked the date of their last menstrual period in lieu of a pregnancy test at each visit. Pregnancy in a participant who has received study intervention is required to be reported within 24 hours of knowledge of the event to the sponsor.

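### For participants of childbearing potential, exclusion criterion 7, Section 5.3 and Section 8.2.9 give three different contraception periods and conflict on method; they need to be reconciled.

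*Protocol*

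**What the plan says.** Section 5.2, exclusion criterion 7, excludes, among others, "anyone unwilling to use contraception for the duration of treatment". The synopsis repeats the criterion.

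Section 5.3 makes contraception a condition of participation for participants of childbearing potential. It runs from the start of study medication, "or 14 days prior to the initiation of study medication for oral contraception", and then "throughout the study period up to 210 days after the last dose of study medication". The section adds "Please refer to the cohort specific package insert for information on contraception requirements". It closes with an entry rule: where reliable compliance is in any doubt, "that participant should not be entered into the study".

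Section 8.2.9 says that female participants able to become pregnant are "required to be on a double barrier birth control method for the duration of the trial in all cohorts". Men with partners of childbearing potential are to be advised according to the drug cohort.

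Two other places bear on how these are read. Section 4.1 says that "study staff shall assess individual participant eligibility using the criteria in" Sections 5.1-5.2 and the supplemental criteria in the cohort appendix. Section 7.2.2.4 says "Participants that discontinue drug will remain on study for 3 years from the date of informed consent", and Section 7.2.3.4 says the same for the μMeta cohorts.

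**The concern.** A contraception rule protects participants only if the site, the consent form and the entry criterion describe the same obligation. Here they cannot, because the protocol states that obligation in three ways. The shortest version is in the numbered criterion that staff check at screening. The two longer versions are in sections that the eligibility instructions do not name.

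Section 5.3 itself warns of possible harm to a fetus, so the time after the last dose is a safety matter. With 25-30 sites planned, different sites may in good faith tell participants different things about how long to continue and by what method. No endpoint, sample size or analysis is affected.

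**Working it through.** There is no statistical figure to reproduce. The check sets the texts side by side and then does day arithmetic.

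**Step 1. Compare the requirements.**

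| Place | Who | Period ends | Method |
|---|---|---|---|
| 5.2 criterion 7, synopsis | Anyone | End of treatment | Not stated |
| 5.3 | Participants of childbearing potential | 210 days after last dose | Oral contraception contemplated; refers to cohort package insert |
| 8.2.9 | Females able to become pregnant | End of the trial, all cohorts | Double barrier |

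All three rows apply together only to participants of childbearing potential. For men, criterion 7 is the only one of these texts that gives a period, so the three-way conflict does not extend to them.

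**Step 2. The firm gap.** Taking treatment to end at the last dose, the difference between 5.3 and criterion 7 is (last dose + 210) − last dose = 210 days, whenever treatment stops. 210 / 7 = 30 weeks; 210 / 30.44 = 6.9 months.

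**Step 3. Bring in 8.2.9, with an assumption.** Section 8.2.9 does not define the duration of the trial. Assume that it means individual participation, which Sections 7.2.2.4 and 7.2.3.4 put at 3 years from consent: 3 × 365 = 1095 days. For an illustrative last dose on day 60 from consent:

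- Criterion 7: day 60.
- Section 5.3: 60 + 210 = day 270.
- Section 8.2.9: day 1095.

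**Step 4. Is one section always the strictest?** No. Under the same assumption, 5.3 and 8.2.9 end together when last dose + 210 = 1095, that is, when the last dose falls on day 1095 − 210 = 885. Before that, 8.2.9 runs longer; after it, 5.3 does. A site cannot settle the matter by always following one section as the most cautious.

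**Step 5. Which text decides entry?** Section 4.1 names 5.1-5.2 and the cohort appendix. The screening steps in 7.2.2.1 and 7.2.3.1 cite 5.1-5.2. None of these names 5.3. A person of childbearing potential who is willing to use contraception only while on treatment therefore does not meet criterion 7, yet falls short of the condition of participation in 5.3.

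**Step 6. Method.** The 14-day lead-in in 5.3 has meaning only if oral contraception is an accepted method. Section 8.2.9 requires double barrier in all cohorts and does not say whether oral contraception may replace it or is additional. The reference in 5.3 to the package insert adds a third possible source.

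**The case against.** The strongest reply is that Section 5.3 already closes the gap. It belongs to the enrolment chapter, makes the longer period a condition of participation, and keeps out anyone whose compliance is in doubt. This stands. A reader might infer from criterion 7 that participants may be entered on a treatment-only commitment, leaving the post-treatment period unprotected. The documents do not support that inference, because the protocol read as a whole forbids it. What remains is that the formal criterion screens for less than 5.3 requires. The 5.3 entry rule also works only if staff know which requirement to apply, and that is the point on which the sections disagree.

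Second, the cohort appendices and package inserts are not available here, and a cohort criterion may state a post-treatment period. This also stands, so it cannot be said that someone would in practice pass screening on the shorter commitment. It does not reconcile the body of the protocol, because 8.2.9 sets its rule for all cohorts.

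Third, the day-1095 figure rests on a reading of an undefined term. Sections 7.2.2.4 and 7.2.3.4 describe the time after stopping drug as follow-up for data entry only, and 5.3 can be read as treating the study period as running to 210 days after the last dose. On that reading 8.2.9 and 5.3 could agree on duration. This is fair. Day 1095 is conditional, but the 210-day difference between criterion 7 and 5.3 and the conflict on method both remain.

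Fourth, criterion 7 also excludes women who plan to become pregnant, a clause that can be read as not limited to treatment. It concerns intention to conceive and sets no contraception period, so it does not supply the missing 210 days.

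**Conclusion.** The point holds as an internal contradiction in a participant-safety instruction, limited to participants of childbearing potential. The firm size is 210 days between the entry criterion and Section 5.3. The spread of day 60, day 270 and day 1095 is an illustration: it assumes a last dose on day 60 and takes the duration of the trial in 8.2.9 to mean participation to 3 years from consent. The conflict on method needs no such assumption.

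It is a matter of alignment: the protocol as a whole does not authorise entry on the shorter commitment. It should still be corrected, because the criterion used at screening is the weakest of the three statements and no section says which one governs.

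**What to change.** Reconcile exclusion criterion 7 in Section 5.2, its copy in the synopsis, Section 5.3 and Section 8.2.9 so that all state one period and name one source for method, either the protocol or the cohort package insert. If a period is tied to the duration of the trial, define that term. State which participants each requirement covers, including what applies to men. Check the cohort appendices and the consent form against the reconciled text.

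The period and the method are clinical choices for the sponsor and are not proposed here. The cost is protocol wording in four places, a check of the consent wording, and the IRB review that any amendment needs. No statistical element changes.

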5.4 PREGNANCY

If a participant inadvertently becomes pregnant while on treatment with study medication, the participant will be immediately discontinued from study treatment. The site will contact the participant at least monthly and document the participant's status until the pregnancy has been completed or terminated. The outcome of the pregnancy will be reported to the Sponsor without delay and within 24 hours if the outcome is a serious adverse event (e.g., death, abortion, congenital anomaly, or other disabling or life-threatening complication to the mother or newborn). The study investigator will make every effort to obtain permission to follow the outcome of the pregnancy and report the condition of the fetus or newborn to the Sponsor.

5.4.1 USE IN NURSING WOMEN

The information contained in this protocol and all other information relevant to this study are confidential and proprietary information of Strata Oncology Inc., except as may be required by federal, state or local laws or regulation, and may not be disclosed to others without prior written permission of Strata.

Page 26 of 56

It is unknown whether study medication is excreted in human milk. Since many drugs are excreted in human milk, and because of the potential for serious adverse reactions in the nursing infant, participants who are breastfeeding are not eligible for enrollment.

5.5 SCREEN FAILURES

Screen failures are defined as individuals who consented to participate in the clinical trial but were not subsequently entered in the study. A minimal set of screen failure information is required to ensure transparent reporting of screen failure participants, to meet the Consolidated Standards of Reporting Trials (CONSORT) publishing requirements and to respond to queries from regulatory authorities. Minimal information includes demography, screen failure details, eligibility criteria, and any serious adverse event (SAE).

Individuals who do not meet the criteria for participation in this trial (screen failure) because of the following may be considered for re-screening:

- Reversible causes of screening failure that have been adequately treated.
- Performance status.
- Stage of disease did not meet inclusion criteria at initial screen but have since progressed and may now meet eligibility criteria.
- Decline or delay in starting due to change in situation (availability, family situation, etc.).

Re-screened participants should be assigned the same study ID number as the initial screening (i.e., re-screened participants do not receive new study IDs).

5.6 STRATEGIES FOR RECRUITMENT AND RETENTION

Individuals will be screened and molecularly identified through standard of care (SOC) CGP testing or other available RNA profiling tests. StrataPATH will leverage the Strata Precision Oncology Network, a collective of >20 large hospital systems in the United States in addition to other academic and large research institutions familiar with biomarker-driven studies. Using this systematized approach, the pre-screened study population will be more likely to represent the demographics of the general advanced cancer population.

StrataEXPRESS (NCT05312307) is a parallel screening study that will be used to identify patients with RNA expression profiles or relevant algorithm scores consistent with eligibility requirements for StrataPATH biomarker/drug treatment cohorts. For StrataEXPRESS, archival tissue from solid tumors will be collected from eligible participants for RNA expression analysis using next-generation sequencing.

The information contained in this protocol and all other information relevant to this study are confidential and proprietary information of Strata Oncology Inc., except as may be required by federal, state or local laws or regulation, and may not be disclosed to others without prior written permission of Strata.

Page 27 of 56

As many of these biomarkers are rare, other testing modalities are acceptable, if, sufficient detail is provided to support sponsor eligibility confirmation.

Pregnant women, those who lack consent capacity, including the mentally ill, prisoners, cognitively impaired participants, children, and employee volunteers will not be included in this study.

Participants will generally be seen and assessed for this research study during their regular clinic visits, reducing the burden to participants and their families.

5.7 PARTICIPANT DISCONTINUATION/WITHDRAWAL FROM THE STUDY

Participants are free to withdraw from participation in the study at any time upon request.

An investigator may discontinue or withdraw a participant from the study for any of the following reasons:

- Pregnancy.
- Significant study intervention non-compliance.
- If any clinical AE, laboratory abnormality, or other medical condition or situation occurs such that continued participation in the study would not be in the best interest of the participant.
- Disease progression which requires discontinuation of the study intervention.
- If the participant meets an exclusion criterion (either newly developed or not previously recognized) that precludes further study participation.
- Participant unable to receive therapy for greater than 2 weeks.
- Death.

The reason for participant discontinuation or withdrawal from the study will be recorded on the CRF. Participants who sign the ICF but do not receive the study intervention may be replaced. Participants who sign the ICF, receive the study intervention, and subsequently withdraw, or are withdrawn or discontinued from the study, will be replaced if the reason for withdrawal is not due to failure to respond. Any participants who withdraw due to progression will be counted in efficacy calculations. Any participant withdrawal and replacement will be detailed in the Screening and Enrollment Log.

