Tumor assessments to support ORR efficacy assessment will be completed as outlined in the Study Schedule of Activities (**Section 7.2**) and recorded in the study database. Study staff will also record information in the study EDC (either manually or through an integrated mechanism) which occur as part of standard of care visits. Standard of care details such as demographics, clinical characteristics, and concomitant medications will be recorded within the study database. Upon identification of any efficacy signal, additional real-world data collection may be requested (i.e., additional medical history and imaging) to support additional analysis and cohort expansion studies. Following completion of or discontinuation from drug, all active study participants will be followed for survival for 3 years from the date of consent.

This study will require reporting of Common Terminology Criteria for Adverse Events (CTCAE) grade 3 and 4 AEs that are possibly, probably, or definitely related to the study treatment. All SAEs, regardless of grade, relatedness to study drug, or expectedness, must be reported, including deaths.

Drug/biomarker cohorts may be added, changed, or discontinued over time. This study may enroll up to 700 participants.

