6.4 STUDY AGENT DISCONTINUATION

Discontinuation of dosing does not mean discontinuation from the study. Remaining study procedures should be completed as indicated by the study protocol regardless of whether the participant is on active treatment. If a clinically significant finding is identified (including, but not limited to, changes from baseline) after enrollment, the investigator or qualified designee will determine if any change in study drug administration is needed. Any new, clinically relevant finding that is both unexpected and thought to be related to the drug will be reported as an SAE under Other Medically Important Event as described in Section 8.2.2. All AEs and SAEs will be reported and captured in the CRF.

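### Section 5.7 lets investigators withdraw participants from the study for events that other sections say do not end follow-up, so survival and next-treatment dates could be lost

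*Protocol*

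**What the plan says.** Section 5.7 is about leaving the study, in its title and in its opening line: "An investigator may discontinue or withdraw a participant from the study for any of the following reasons". One listed reason is "Disease progression which requires discontinuation of the study intervention". Others are pregnancy, significant non-compliance with the study intervention, and being unable to receive therapy for more than 2 weeks. On the data of those who leave, it says "Any participants who withdraw due to progression will be counted in efficacy calculations". It is silent on survival follow-up.

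Other sections keep these participants on study:

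- Section 6.4: "Discontinuation of dosing does not mean discontinuation from the study". It adds that remaining study procedures should be completed whether or not the participant is on treatment.
- Section 7.2.2.4, repeated for the μMeta cohorts in 7.2.3.4: "Participants that discontinue drug will remain on study for 3 years from the date of informed consent". Survival status and anticancer therapies are entered every 3 months. Both sections name progression as a reason for stopping drug.
- Section 7.3.1: after confirmed progression, the participant must move into the post-treatment follow-up period.
- Section 8.2.9: a participant who becomes pregnant "will not be discontinued from the study to allow for tracking of event outcome".

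Overall survival is a secondary endpoint in both cohort types (Section 3.1, Tables A and B). Time to next treatment, ending at the next systemic treatment or death, is secondary in the tdMeta cohorts. Section 9.3.2 summarises both by Kaplan-Meier.

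**The concern.** Stopping the drug and leaving the study are different events with different consequences for the data. Section 5.7 puts several drug-stopping events on a list of reasons for leaving the study, so two sites can treat the same participant differently and each be following the protocol.

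What is at stake is the data after progression. Kaplan-Meier assumes that a censored participant has the same future risk as those still followed. A participant withdrawn at progression is at higher risk of death than the average participant still under observation, so that censoring is informative and pushes the survival curve up. Time to next treatment is exposed too, because the next-therapy date and the death date come from the same follow-up. No rule in a statistical analysis plan can recover dates that were never collected. Section 3.2.1 also uses survival as the established endpoint beside which time to next treatment and time to discontinuation are to be examined as surrogates.

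**Working it through.** **Step 1. The passages side by side**

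| Event | Section 5.7 | Elsewhere in the protocol | Conflict? |
|---|---|---|---|
| Progression requiring drug stop | May be withdrawn from the study | On study 3 years from consent (7.2.2.4, 7.2.3.4); enters post-treatment follow-up once confirmed (7.3.1) | Yes |
| Non-compliance; more than 2 weeks without therapy | May be withdrawn from the study | Stopping drug is not leaving the study (6.4); no exception by reason in 7.2.2.4 or 7.2.3.4 | Yes |
| Pregnancy | May be withdrawn from the study | Not discontinued from the study (8.2.9); treatment stopped, at least monthly contact until the pregnancy ends, outcome reported (5.4) | Yes, literally |
| Adverse event or other condition | May be withdrawn only where continued participation is not in the participant's best interest | Drug stop for an adverse event does not end assessments (7.3.1) | Not plainly; the test is at study level |

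Sections 7.2.2.4 and 7.2.3.4 refer to Section 5.5 for stopping drug at the physician's discretion. Section 5.5 covers screen failures. The only list of investigator discontinuation reasons is in 5.7, so a site looking for the drug-stopping text is likely to land on a list worded as study withdrawal.

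**Step 2. Does 5.7 secure the dates?** Counting progression withdrawals in the efficacy calculations keeps them in the response rate. It does not provide a death date or a next-therapy date.

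**Step 3. Size.** The protocol has no survival figure to reproduce: it gives no time to progression, post-progression survival or withdrawal share. The following inputs are assumptions.

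- Time to progression is exponential with median 4 months: λ1 = ln 2 / 4.
- Post-progression survival is exponential with median 6 months: λ2 = ln 2 / 6.
- No one dies before progression.
- A random share f is censored at progression. Write g = 1 − f.

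Then λ1/(λ1 − λ2) = (1/4)/(1/4 − 1/6) = 3 and λ2/(λ1 − λ2) = 2. The proportion alive without progression is P0 = exp(−λ1 t), and alive after it is P1 = 3[exp(−λ2 t) − exp(−λ1 t)]. Kaplan-Meier estimates the curve with hazard λ2·gP1/(P0 + gP1). With y = exp(−(λ1 − λ2)t), this integrates to

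S(t) = y² × [3g − (3g − 1)y]^(2/(3g − 1)).

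At 12 months y = 2^(−12 × (1/4 − 1/6)) = 0.5, so S(12) = 0.25 × [(3g + 1)/2]^(2/(3g − 1)).

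| Share withdrawn at progression | S(12) | Shift | Median (solve S = 0.5) |
|---|---|---|---|
| 0% (true value) | 0.25 × 2^1 = 50.0% | – | 12.0 months |
| 10% | 0.25 × 1.85^(2/1.7) = 0.25 × 2.062 = 51.6% | +1.6 points | 12.4 months |
| 25% | 0.25 × 1.625^1.6 = 0.25 × 2.175 = 54.4% | +4.4 points | 13.0 months |

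A simulation of 400,000 participants under the same assumptions gave 49.9%, 51.5% and 54.3%, which are the same shifts.

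**Step 4. Sensitivity.** A second simulation (200,000 participants, 36-month cut-off) allowed deaths before progression. It kept the 4-month median to progression, with a median of 24 to 36 months to death without progression and 6 to 10 months after progression. Across three scenarios the 12-month shift was 0.5 to 0.9 points with 10% of progressors withdrawn and 1.5 to 2.5 points with 25%. The direction was upward each time, but the size was smaller.

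**Step 5. Scale.** With 35 participants and complete follow-up, the standard error of a 50% survival estimate is √(0.5 × 0.5 / 35) = 8.5 points. A shift of 1.6 to 4.4 points is about 0.2 to 0.5 of one standard error.

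**The case against.** The strongest answer is that the specific text wins. Section 5.7 only permits withdrawal, whereas 7.2.2.4, 7.2.3.4 and 7.3.1 are directive for participants who stop drug at progression, and the schedule notes to Tables C and D run post-treatment follow-up every 3 months to 3 years or death. A site working from the schedule would keep a progressor in follow-up. This has force: it makes the bias possible, not expected. It does not remove the conflict, because 5.7 gives an equally valid licence to end participation and nothing says which section prevails.

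Four stronger readings are tempting, and the documents do not support them:

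- *That Section 4.1 leaves out those off drug.* It says "all active study participants will be followed for survival for 3 years from the date of consent", but that sentence opens by referring to completion of or discontinuation from drug. The word *active* therefore already covers people off treatment, as it does in 7.3.1.
- *That adverse events are listed as a plain drug-stopping reason.* The bullet beginning "If any clinical AE, laboratory abnormality, or other medical condition or situation occurs" applies only when staying in the study is against the participant's interest. That is a legitimate study-level test.
- *That pregnancy outcomes would go uncollected.* The wording conflict with 8.2.9 is literal, but Section 5.4 separately requires contact until the pregnancy ends and a report of its outcome. The effect on survival estimates is small.
- *That survival will be substantially overstated.* Large shifts need a large share withdrawn at progression, and the protocol gives no reason to expect one in view of its follow-up rules.

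It is also true that survival is descriptive here. There is no survival hypothesis, and the two-stage rule in Section 9.1 uses response only.

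**Conclusion.** The point holds as an inconsistency in the protocol with a possible effect on the data. Section 5.7 allows study withdrawal for progression, non-compliance, more than 2 weeks without therapy and pregnancy, and does not preserve survival follow-up. Sections 6.4, 7.2.2.4, 7.2.3.4, 7.3.1 and 8.2.9 say otherwise.

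If sites use the option at progression and stop collecting data, Kaplan-Meier survival could be biased upward and time to next treatment could lose next-treatment or death dates. The size cannot be derived from the protocol. The illustration gives about 1.6 to 4.4 points at 12 months for 10% to 25% withdrawn. It rests on exponential times, no death before progression and random withdrawal among progressors; allowing earlier deaths reduces it to about 0.5 to 2.5 points. That is within sampling error for one cohort, but it acts in one direction wherever the option is used. No primary decision depends on it. It is worth correcting because the lost data cannot be recovered later and the correction is simple.

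**What to change.** Reconcile Section 5.7 with 6.4, 7.2.2.4, 7.2.3.4, 7.3.1 and 8.2.9 by treating discontinuation of study treatment and withdrawal from the study as two separate events. Leave every clinical rule for stopping drug as it is. Do not simply relabel the whole 5.7 list as reasons for stopping drug: that would set clinical stopping rules and would misplace the best-interest bullet.

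Add to 5.7 that, whatever the reason for stopping treatment, the scheduled 3-monthly collection of survival status and next anticancer therapy continues, with pregnancy outcome under 5.4. It ends only at death, withdrawal of consent, loss to follow-up, 3 years from consent or study closure. The reference to Section 5.5 in 7.2.2.4 and 7.2.3.4 can be corrected in the same edit. Section 4.1 needs no change to the word *active*.

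The cost is protocol wording in an amendment. The follow-up visits and data entry are already in the schedule, so there is no added visit, procedure or sample size.
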